### **Research Procedure:**

A medial parapatellar approach will be performed. All closures will be performed in 3 layers, with the knee in approximately 90° of flexion to minimize potential imbrication of the capsule. For the traditional closure (control group), the arthrotomy (deep layer) is repaired using number 1 Vicryl followed by closure of the intermediate layer with a 2-0 Vicryl and a subcutaneous layer with a 2-0 Monocryl followed by steri-strips and adhesive.

For the active arm of the study, wound closure will be performed similarly in 3 layers with the use of barbed equivalents at every layer: STRATAFIX symmetric PDS Plus #1 will be used to close the capsule (See Table 2). The subcutaneous layer will be then closed with simple interrupted knots using number 2-0 braided absorbable sutures (Vicryl), followed by closure of the subcutaneous layer using a number 2-0 monofilament absorbable suture with inverted interrupted knots (Monocryl, Ethicon; Johnson & Johnson) followed by the use of steri-strips and adhesive (See table 2).

Closure with the bidirectional barbed suture involves starting at the midpoint of the wound and proceeded simultaneously both proximally and distally to the ends. At the ends of the wounds, the suture is backstitched at this subcuticular level (2-3 throws) toward the midpoint for

further reinforcement before bringing the needle out through the skin; the suture is then cut flush with the skin tissue at its free end. With each throw, the leading end of the suture is pulled with only enough tension to engage the barbs with the surrounding tissue, thereby locking the wound edges into approximation. As with the traditional closure and in concordance with our routine protocol, barbed closures were finished with skin steri-strips and adhesive.

Table 2: Suture Type for Closure Following Total Knee Arthroplasty.				
Layer	Control Group	Active Group		
Capsule	Vicryl #1 (J947H#1)	STRATAFIX (SXPP1A04#1)		
Subcutaneous	Vicryl 2-0 (J945H 2-0)	Vicryl 2-0 (J945H 2-0)		
Subcuticular	Monocryl 4-0 (Y496H)	Monocryl 4-0 (Y496H)		
Skin	Steri-strips, glue (Standard of care)	Steri-strips, glue (Standard of care)		

#### **Patient Protection:**

All data collection sheets will be de-identified. All patients will be assigned a study ID. All data collected will be entered into Excel sheet and stored on Cleveland Clinic secure computers. Only members of the study team (listed on the IRB application) will have access to protected health information of patients included in this study.

### **Safety Monitoring Plan**

Procedural safety will be documented in this study through patient and surgeon reported adverse events. AEs will be documented for all cases in this study. An Unanticipated Problem involving risks to participants or others is any event that (1) is unforeseen, (2) caused harm or placed a person at increased risk of harm, and (3) is related to the research procedures.

An Adverse Event (AE) is any untoward or unfavorable medical occurrence, including any abnormal sign (for example, abnormal physical exam or laboratory finding), symptoms, or disease. Adverse events can encompass both physical and psychological harms. An Internal Adverse Event (AE) is an untoward medical occurrence, which occurs to participants in research conducted by Cleveland Clinic and/or Cleveland Clinic is the IRB of record. External Adverse Event (AE) is an untoward medical occurrence experienced by subjects enrolled at other

institutions for the same study approved at Cleveland Clinic or a different study using the same study drug/device. A Serious Adverse Event (SAE) is any adverse experience that results in any of the following outcomes:

- Death
- A life-threatening experience
- Inpatient hospitalization or prolongation of existing hospitalization
- A persistent or significant disability/incapacity.
- A congenital anomaly/birth defect
- Important medical events that may not result in death, be life-threatening, or require hospitalization may be considered a serious adverse drug experience when, based upon appropriate medical judgment, they may jeopardize the patient or subject and may require medical or surgical intervention to prevent one of the outcomes listed in this definition.

An Unexpected Adverse Event means any AE not previously known or included in the current Investigator's Brochure, consent form or other risk information.

Related/Possibly Related means there must be reasonable evidence to suggest the event was caused by the drug, device or investigational intervention.

- 1. Internal Serious Adverse Events (events that occur to participants enrolled in research being conducted by Cleveland Clinic or when Cleveland Clinic is the IRB of record) must be promptly reported to the IRB using the IRB AE Report Form within 10 working days from discovery/awareness which meet any of the following criteria as assessed by the PI/Co-I:
  - a) Serious, Unexpected and Related/Possibly Related.
  - b) AE's determined to be occurring at a significantly higher frequency or severity than expected.
  - c) Other Unexpected AE's, regardless of severity, that changes the risk benefit ratio of the study and results in changes to the Research Protocol or Informed Consent process/document.

All Internal SAEs are also reported at continuing review using the AE Summary Log.

- **2. External Serious Adverse Events** (events experienced by subjects enrolled at other institutions for the same study approved at Cleveland Clinic or a different study using the same study device/drug) are reportable to the IRB using the IRB AE Report Form within 10 working days from discovery/awareness when:
  - a. The External SAE report includes reasonable evidence as assessed by a central monitoring entity [Coordinating or Statistical Center, or a Data Safety

Monitoring Board (DSMB) or Data Monitoring Committee (DMC)] that the event is Serious, Unexpected, and Related/Possibly Related AND places the subjects or others at a greater risk of physical or psychological harm than was previously known or recognized. This will require a change in the protocol and/or consent document.

- b. External SAE reports provided by the Sponsor to the investigator indicating the event is Serious, Unexpected and Related/Possibly related but without reasonable evidence or DSMB/DMC determination of greater risk are not reportable to the IRB within the 10 day window. Without Sponsor evidence or assessment the implications of the event cannot be determined by the research team and therefore need not be reviewed. These SAE' shall be placed on the AE Summary log to be submitted at the annual continuing renewal.
- **3. DEATHS** are to be reported to the IRB using the IRB AE Report Form according to the following guidelines:
  - a) Internal Death:
    - Related/possibly related whether expected or unexpected—within 5 working days from discovery/awareness
    - Not related and expected at time of continuing review
    - Not related and unexpected at time of continuing review except cancer studies.
    - Cancer: Not related and unexpected within 10 working days from discovery/awareness

### b) External Death:

Related/possibly related and unexpected – within 5 working days from discovery/awareness not related whether expected or unexpected – at time of continuing review related/possibly related and expected – at time of continuing review

- c) ALL Deaths are also reported at time of continuing review using the AE summary log.
- **4. Non-serious Adverse events** (Internal and External) that are both Related/Possibly related and unexpected are reported on the AE Summary Log at time of continuing review to assess trends.
- **5.** An IRB staff (a qualified, licensed practitioner assigned to this function by the IRB chair and IRB Executive Director) reviews Adverse Event Reports to determine whether they represent Unanticipated Problem Involving Risks to Participants or Others. Events that are assessed, by either the IRB Staff or Investigator, to place subjects or others at a greater risk of

harm than was previously known or recognized, or changes the risk/benefit ratio of the study, or requires a change in the protocol and/or consent document are referred to Full Board for review under Policy #70. Events that do not involve risk to Participants or Others or changes to the informed consent or protocol do not require further review. Investigators are informed of the determination and the IRB file is updated.

**6.** The AE Summary Log is reviewed by the IRB at the time of continuing review to identify trends in frequency and severity which may impact subject safety.

This study is an Investigator Initiated research trial. Each study site will be considered its own regulatory sponsor and is responsible for internal data monitoring and any study reporting required by ClinicalTrials.gov.

## **Data Analysis:**

Unless otherwise indicated, all testing of statistical significance will be two-sided, and a difference resulting in a p-value of less than or equal to 0.05 will be considered statistically significant. Also, after each analysis, General Linear Models (GLM) will be used to control for possible confounders, including BMI, gender, age and ethnicity.

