## **Background and Significance/Preliminary Studies:**

Preclinical and biomechanical studies have demonstrated efficacy in cosmetic skin and deep tissue closures.[1], [2] In addition, barbed sutures have been shown to provide water-tight closure and wound strength comparable to or superior to closure with conventional sutures. Many comparative studies have been published contrasting barbed sutures to conventional closure techniques in multiple surgical fields. [3], [4]

Various studies have evaluated the outcomes of different barbed suture devices, however there are no reports assessing the length of closure times using STRATAFIX (Ethicon, Johnson and Johnson, Somerville, New Jersey) Knotless Tissue Control Devices during deep closure in total hip arthroplasty. Stephens et al. [5] performed a prospective randomized study of 500 total knee arthroplasty patients who received either barbed suture (250) or conventional sutures (250) for deep closure of the surgical wound. The mean operating time was significantly shorter in the barbed group as compared to conventional group (64.3 vs 68.1 minutes, p=<0.001). In a study of 80 TKA (61 barbed, 19 conventional deep sutures) and 54 THA patients (37 barbed, 17 conventional deep sutures), Smith et al. [6] found significantly shorter closure time in the barbed suture group (16.78 vs. 26.5 minutes, p<0.001). One study reports one the use of Stratafix suture for intracorporeal suturing in myomectomy. Giampaolino et al. [7] performed a prospective randomized study on 47 patients and evaluated the mean operative time for laparoscopic posterior myomectomy using Stratafix or conventional suture for intracorporeal suturing. There was a significant decrease in mean operative time associated with use of Stratafix suture as compared to conventional suture (66.3 vs 73 minutes, p=0.005).

This prospective randomized single-center study will examine the outcomes, mainly closure time, of deep closure during total knee arthroplasty using the STRATAFIX Symmetric PDS Plus (Ethicon, Johnson and Johnson, Somerville, New Jersey) barbed suture compared to interrupted VICRYL suture (Ethicon, Johnson and Johnson, Somerville, New Jersey).

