## **Study Design:**

In this prospective study examining the deep closure during total knee arthroplasty, active subjects will receive the STRATAFIX Symmetric PDS Plus (Ethicon, Johnson and Johnson, Somerville, New Jersey) suture while the control subjects will receive interrupted VICRYL suture (Ethicon, Johnson and Johnson, Somerville, New Jersey). Superficial closure will be the standard of care for both groups.

The purpose of this study is to compare end points (see below):

- The primary endpoint of the study will be closure time and operative time.
- **Secondary endpoints** will examine: wound complications, costs comparison between the two techniques.

Post-operatively, patients will be assessed at clinic visits at 6 weeks and 3 months. At these time points, we will assess (**Table 1**):

Table 1.

REQUIRED STUDIES	Pre-Op	Intra- operative	6 week post-op	3 month post-op
Informed Consent	X			
Length of surgery time		X		
Length of closure time		X		
Amount of suture material used		X		
Surgeon experience level		X		
Wound complications			x	X

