# **Randomization procedures:**

Patients will be randomized to either arm of the study as follows: sealed envelopes in a random order will be used to place study participants in either the barbed suture arm or in the traditional suture arm of the study. Patients will be randomized in a one to one ratio. At the commencement of each arthroplasty, a random envelope will be drawn which dictated the type of suture to be used, thus blinding the patients to the type of suture they received.

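### Surgeon experience level is recorded but is not a named GLM covariate for closure or operative time, and the plan does not say which analysis decides the primary comparison

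*Combined protocol and SAP*

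**What the plan says.** Under Study Design, "The primary endpoint of the study will be closure time and operative time". Table 1 in the same section lists "Surgeon experience level" among the required items, marked as intra-operative, without a scale or categories. No other section gives that item a use.

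The Data Analysis section is the whole analysis plan. It sets two-sided testing at p ≤ 0.05 and adds that, once each analysis is done, "General Linear Models (GLM) will be used to control for possible confounders, including BMI, gender, age and ethnicity". The first analysis is not described, and neither it nor the GLM is called primary.

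Under Randomization procedures, "sealed envelopes in a random order will be used to place study participants in either the barbed suture arm or in the traditional suture arm". The ratio is 1:1 and no stratification is stated. The sample is 60 subjects, described as a pilot.

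**The concern.** The two primary outcomes time a task done by an operator. All four named covariates describe the patient. The one operator characteristic that the trial collects, and a plausible driver of both times, is not named. Allocation is not stratified on it either.

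Three things are at stake:

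- **Precision.** If experience explains a material share of the variation in time, leaving it out of the GLM widens the interval.
- **Chance imbalance.** With 30 per arm and no stratification, the arms may differ in experience by luck, and no correction is planned.
- **Choice of result.** An open covariate list and an undesignated primary analysis allow at least two p-values per endpoint, judged against a fixed threshold, with no rule for which one counts.

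**Working it through.** The plan gives no SD, effect size or power, so there is no figure of its own to reproduce. Everything below is illustrative.

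**SD limits from the Background section.** These assume a pooled-variance t-test, because the section names no test.

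- Closure time: the cited joint-replacement study "found significantly shorter closure time in the barbed suture group (16.78 vs. 26.5 minutes, p<0.001"). The difference is 26.5 − 16.78 = 9.72 min. The groups are 61 + 37 = 98 barbed and 19 + 17 = 36 conventional, knees and hips pooled. p = 0.001 corresponds to t(132) = 3.366, so SE ≤ 9.72/3.366 = 2.888 and SD ≤ 2.888/√(1/98 + 1/36) = 14.8 min.
- Operative time: in the cited 500-patient knee trial, "The mean operating time was significantly shorter in the barbed group as compared to conventional group (64.3 vs 68.1 minutes, p=<0.001"). The difference is 68.1 − 64.3 = 3.8 min, with 250 per group. t(498) = 3.310, so SE ≤ 1.148 and SD ≤ 1.148/√(2/250) = 12.8 min.

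**Precision model.** There are 30 per arm and k covariates, each costing one degree of freedom.

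- Variance of the difference = SD² × (1 − R²) × (2/30) × 57/(57 − k), on 58 − k degrees of freedom. The last factor is the average cost of chance imbalance.
- R² is the share of variance explained by experience: share × (1 − share) × gap²/SD². The gap is the difference in mean time between two experience levels.
- The four patient covariates are treated as noise. Power is from the noncentral t distribution.

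Closure time, SD 14.8, 50/50 split, true difference 9.72 min:

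| Analysis | R² | 95% half-width (min) | Power |
|---|---|---|---|
| Unadjusted (k = 0) | – | 7.65 | 71% |
| Planned four-covariate GLM (k = 4) | – | 7.95 | 67% |
| Plus experience (k = 5), gap 0 | 0 | 8.02 | 66% |
| Plus experience, gap 3 min | 0.010 | 7.98 | 67% |
| Plus experience, gap 10 min | 0.114 | 7.55 | 72% |

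**Break-even.** The 97.5% t quantiles are 2.0017 (58 df), 2.0049 (54 df) and 2.0057 (53 df). The gap at break-even is 2 × SD × √R².

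- Against the planned GLM: R² = 1 − (2.0049/2.0057)² × 52/53 = 0.020. Gap = 29.6 × √0.0197 = 4.2 min.
- Against the unadjusted test: R² = 1 − (2.0017/2.0057)² × 52/57 = 0.091. Gap = 29.6 × √0.0914 = 8.9 min.

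The break-even shares do not depend on the SD; the gaps scale with it. At SD 10 they are about 2.8 and 6.0 min.

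**Operative time**, SD 12.8, difference 3.8 min, same formula: half-width 6.62 unadjusted and 6.87 for the planned GLM. With experience added it is 6.94, 6.89 and 6.39 at gaps of 0, 3 and 10 min. Power is 19% to 22% throughout.

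**Chance imbalance.** With a two-level factor at 50% and independent binomial counts of 30 per arm, the arms differ by 20 percentage points or more in 15.5% of randomizations.

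**Choosing between p-values.** Simulation of 200,000 null trials, N = 60, one endpoint, four noise covariates, SD 14.8, 50/50 split:

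- any single analysis: 5.0% to 5.1%
- smaller of the unadjusted and four-covariate GLM p-values: 6.2%
- also allowing a GLM with experience: 6.6%, 6.7% and 7.6% at gaps of 0, 3 and 10 min

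Separate runs of the two-analysis choice gave 5.9% to 6.1%.

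**The case against.** Much of the case against stands. Randomization protects the comparison, an unadjusted test would be valid, and the word introducing the covariate list leaves it open, so experience is not excluded. The precision gain rests on assumed gaps and on SD upper limits. Patient covariates that predict nothing cost more than a weak experience effect returns. The type I excess is about one percentage point, and most of it comes from having two analyses rather than from experience. The sequence of analysis and then GLM can be read as making the GLM supportive, although no sentence says so. The trial is also a pilot, which lowers the stakes; the plan nevertheless sets a significance threshold.

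A reader might infer more, in three ways that the documents do not support:

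- **That the omission biases the result or inflates its error rate.** In a 1:1 randomized comparison it does neither. Only choosing among analyses after seeing the data inflates type I error.
- **That the adjusted model is clearly the better primary analysis.** The table does not show this. The documents give no evidence on how prognostic experience, BMI, age, gender or ethnicity are for these times.
- **That the person closing might be picked once the allocation is known.** The plan says that "At the commencement of each arthroplasty, a random envelope will be drawn" and is silent on who closes. Silence is not evidence that this happens, and requiring earlier assignment would constrain theatre staffing.

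**Conclusion.** The point holds as a gap in prespecification with modest consequences. Relative to the GLM already planned, adding experience costs almost nothing if experience is irrelevant (half-width 7.95 to 8.02 min). It gains once experience explains about 2% of variance, a gap of about 4 min at SD 14.8. Relative to an unadjusted test, the five-covariate model gains only above about 9%, a gap of about 9 min, unless the patient covariates help. Leaving the deciding analysis open permits about 6% type I error for one endpoint, and 6.6% to 7.6% if experience may be added post hoc, against 5% for any single fixed analysis.

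These sizes assume two experience levels, an even split, noise patient covariates, one degree of freedom for ethnicity, and SDs back-calculated from cited p-values. If all cases are done at one experience level, there is no precision to gain.

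**What to change.** In Data Analysis:

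1. Add surgeon experience level, with its categories stated in advance, to the GLM covariates for closure time and operative time.
2. Close the covariate list.
3. Describe the first analysis, and state which single analysis is primary and which is supportive. Either the unadjusted or the adjusted analysis can be defended; what matters is that one is fixed beforehand.

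The cost is one covariate name, a short definition of categories and a few sentences on the analyses. No new data item is needed, because Table 1 already requires it. The statistical price is about one degree of freedom for two levels.

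This does not settle multiplicity across the two primary endpoints. Two independent tests at 0.05 would give 1 − 0.95² = 9.75%, and that needs its own decision.

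### Closure time is a primary endpoint, but wound length is neither recorded nor named as a covariate, which costs precision and a comparability check

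*Combined protocol and SAP*

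**What the plan says.** Study Design states: "The primary endpoint of the study will be closure time and operative time". The intra-operative rows of Table 1 are surgery time, "Length of closure time", "Amount of suture material used" and "Surgeon experience level". None is a length of incision, wound or arthrotomy.

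Research Procedure fixes the approach ("A medial parapatellar approach will be performed") without giving or asking for a length. It describes the barbed closure as "starting at the midpoint of the wound and proceeded simultaneously both proximally and distally to the ends"; it gives no corresponding path for the interrupted control closure. In Table 2 of that section the arms differ only at the capsule.

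Randomization procedures sets a 1:1 ratio and says: "At the commencement of each arthroplasty, a random envelope will be drawn which dictated the type of suture to be used". It mentions blinding of patients and of nobody else.

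Data Analysis says that, after each analysis, general linear models will "control for possible confounders, including BMI, gender, age and ethnicity". The list is open-ended, and length is not on it.

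**The concern.** A longer wound plausibly takes longer to close with either suture. That is a premise about surgery rather than a statement in the documents, but it is a mild one. If it holds, three things follow.

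- Variation in length between patients adds noise to closure time, and the planned model can remove only the part that BMI, gender and age happen to carry.
- With 30 patients per arm, the arms can differ in mean length by chance, and nothing adjusts for it. The same applies to the amount of suture used, which bears on the cost comparison.
- The operator can know the arm while the wound is being made. Without a recorded length, the trial could not show that wounds were of similar length in the two arms.

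The open wording of the covariate list does not rescue this, because a length that was never measured cannot be added at analysis. Suture amount cannot stand in for it: it is observed after allocation and depends on the suture.

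**Working it through.** **Inputs from the documents.** 60 subjects (Sample), 1:1 allocation (Randomization procedures), hence 30 per arm; BMI, gender, age and ethnicity as named covariates (Data Analysis). The plan gives no standard deviation, effect size or power for the 60, so there is no figure of its own to reproduce.

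**Assumed.** r, the within-arm correlation of length with closure time, taken as 0.3 and 0.5. The documents give no value.

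**Step 1: is the comparison biased without length?** Trials of 30 per arm were simulated with 40,000 replicates per setting, r = 0.3, 0.5 and 0.7, and length unaffected by arm. With no true effect, the mean unadjusted difference was 0.00 SD and the two-sided 5% test rejected in 4.8% to 5.1% of trials. With a true difference of 0.72 SD, unadjusted and adjusted estimates both averaged 0.72 to 0.73 SD. Randomisation does its work: no bias and no inflation of type I error.

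**Step 2: chance imbalance.** The standardised difference in mean length between arms has SD √(2/30) = 0.26, so its 95% range is about ±1.96 × 0.258 = ±0.51. The resulting shift in one trial's closure-time difference has SD r × 0.258:

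- r = 0.3: 0.08 SD of closure time
- r = 0.5: 0.13 SD of closure time

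The unadjusted standard error already allows for this variation. Adjustment would remove it.

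**Step 3: gain with no other covariates.** Variance ratio = (1 − r²) × 57/56, where 57/56 is the price of one covariate at n = 60.

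- r = 0.3: 0.91 × 1.018 = 0.926, a cut of about 7%
- r = 0.5: 0.75 × 1.018 = 0.763, a cut of about 24%

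**Step 4: gain beyond BMI, gender and age.** This is the relevant comparison for the planned model. Assume, for illustration, that these three explain half of the variance of length and affect closure time only through length. They then already remove r²/2 of the closure-time variance, leaving 1 − r²/2, and adding length takes it to 1 − r².

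- r = 0.5: 0.75 / 0.875 = 0.857, a cut of about 14%, against 25% (1 − 0.75) with no other covariates, both before the degrees-of-freedom correction
- r = 0.3: 0.91 / 0.955 = 0.953, a cut of about 5% before that correction

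One more term beside arm and three covariates multiplies the variance by about 54/53 = 1.019. The cuts become about 13% (0.857 × 1.019 = 0.873) and about 3% (0.953 × 1.019 = 0.971).

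**Step 5: does ethnicity stand in the way?** Entered as 1 to 4 indicator terms and unrelated to closure time, it lowers the residual degrees of freedom from 55 to between 54 and 51. The standard error rises by a factor √(54/53) = 1.009 to √(54/50) = 1.039, that is by about 1% to 4%. Sixty patients can carry both ethnicity and length.

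**The case against.** The strongest reply is that randomisation already protects the comparison. A reader might infer from the missing length that the closure-time result is confounded, mixing suture speed with wound size. The documents do not support that: allocation is random and 1:1, and step 1 shows no bias. This objection stands in full.

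Other points on that side:

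- *The gain is assumed.* Every r here is an assumption, and the figures without covariates match no analysis that uses the named ones. Converting them into an equivalent number of patients would overstate the benefit. The models also follow each main analysis, so a new covariate sharpens the adjusted result and leaves an unadjusted one unchanged. All of this stands.
- *Table 1 is not a full data list.* It omits BMI, gender, age and ethnicity, which the analysis will use. That is fair, but those four are named in Data Analysis, whereas length is named nowhere.
- *Operator choice is speculative.* Nothing suggests that the suture influences the incision, and one approach is specified for all cases. A marked length taken before the envelope also could not correct for a later change. Both stand; only arthrotomy length reported by arm could reveal such a difference.
- *Wrong layer.* Skin length is a proxy for arthrotomy length, and the arms differ only at the capsule. This may lower r, but it does not remove the case for measuring.
- *Ethnicity.* A reader might infer that it takes the place of length in the model. It does not: the list is open and the cost is small.
- *Surgeon experience* is recorded but not among the named covariates. That is a separate, compatible point, and unlike length it can be recovered at analysis.

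**Conclusion.** The point holds as a minor one. On the documents as written, a plausible driver of a primary endpoint is neither measured nor adjusted for. The loss is one of precision, of adjustment for chance imbalance, and of the ability to show that wounds were comparable when the arm is known from the start of surgery. It is not evidence of bias.

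The size turns on the partial correlation of length with closure time given BMI, gender and age, which is unknown. Under the illustration in step 4, the variance reduction in the adjusted analysis would be about 3% to 13% for r between 0.3 and 0.5. It would be larger if the named covariates say little about length, up to roughly the 7% to 24% of step 3. If length turned out to be unrelated to closure time, including it would cost about 2% in variance.

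**What to change.** - In Table 1 of Study Design, add an intra-operative item: *planned (marked) incision length, cm, recorded before the envelope is opened*. Taken at that moment, it cannot be affected by allocation.
- In Data Analysis, add this length to the covariates of the general linear models for closure time and suture amount. Ethnicity can stay.
- Also record arthrotomy length at the start of closure and report it by arm as a descriptive comparability check. Do not adjust for it, since it is measured after the arm is known.

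Cost: two ruler readings per case, both outside the timed closure, one model degree of freedom, and a one-line change to each of the two sections.
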